Sixty fathers, their female co-parent and youngest child will be recruited to participate in the study. At the time of intake at Westcare's Emerge Program and Salvation Army's Residential Substance Abuse Rehabilitation Program, fathers will be provided flyers about the study. Men who express an interest in participating in a parenting program as part of their treatment will fill out an initial interest form with their counselors (including their name, arrival and discharge date, information about how often they're in contact with their children) and have their counselors submit this form to the Project Coordinator. The Project Coordinator will schedule a screening with the potential participant and will be asked to sign a consent form,

and to sign a release of information to review their SA treatment and criminal history. Men will be told that his questionnaire and records will be reviewed and will be contacted further if considered eligible by the PI based on the study's requirements.

This will provide the opportunity to contact the mother to conduct a phone screening in regards to IPV history and willingness to participate. If the mother indicates an IPV history that involved hospitalization or strangulation or a current full no contact protective order, he will be notified that based on the demographic screening, he is not eligible for the study. If the father is eligible and agrees to participate in the study, the research assistant will contact the father to set up a baseline assessment and the co-parent will be contacted to set up a baseline interview by phone or in-person if she wants to participate. If the father is not eligible for the program we will remove the bottom portion of his screening form that includes personal information (name, arrival and discharge date, and WestCare or Salvation Army counselor information) and shred it. The top portion including de-identified information (IPV history and contact with children) will be kept to keep track of the number of referrals compared to the number of participants in the program.

Mothers of the father's youngest child will be recruited in several ways:

1. When she visits the facility she will be approached by study staff in person.
2. She will be mailed study flyers asking her to contact the research office.
3. Westcare or Salvation Army staff will call mothers and ask permission for study staff to contact them to tell them about the study.

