Fathers will meet the following Inclusion criteria: (1) current DSM-5 criteria for substance use disorder of alcohol, cocaine, marijuana, amphetamines, or opiates at the time of admission to Westcare or Salvation Army; (2) report physical or psychological violence in an intimate relationship within 12 months of admission to the program (based on court/police records or self- report); and (3) be expecting his first biological child in the next 6 months (current or former partner is pregnant), have at least one biological child under the age of 15 with whom they

lived or had at least once per month contact prior to admission to Westcare or Salvation Army. Each will agree to have their female co-parents contacted for participation as collateral informants and will provide the contact information. If a participant has more than one child in the age range, the youngest child will be the target of assessment. Female co-parents (the target children's mothers) will be invited to participate as collateral informants on research assessments and to participate in a portion (2 -4) of the intervention sessions. If a female co-parent does not consent to participate, a male participant will still be allowed to enroll in the study if he meets eligibility criteria.

Individuals will be excluded who: 1) Have histories of severe physical violence against a female partner (e.g. strangulation, causing hospitalization) based on police records, self or partner reports; 2) Men who have an active FULL/NO CONTACT protective order pertaining to their partner or child (Westcare and Salvation Army have access to criminal record/court information for all of its residential clients. Participants will sign releases of information during informed consent to allow the study team to access this information to determine eligibility); 3) Have cognitive impairment (a mini mental state score <25); 4) Have major medical complications such as a head injury or HIV dementia that may also be a confound in the study interventions; 5) Have current untreated psychotic or bipolar disorder (reported by history, as part of the Westcare or Salvation Army record, or self-report); or 6) Are currently suicidal or homicidal. If potential participants have a prior diagnosis of bipolar or psychotic disorder that is currently treated and symptoms are well managed based on initial study interview and after collateral contact with the Westcare or Salvation Army treatment teams, they may participate in the study.

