Table 1. Standardized Measures and administration for Randomized Trial

Instrument	Rater	Reliability	Base-line	Monthly During Intervention	Post Residential Intervention 12 weeks	Post Intervention 16 weeks	3 month follow-up 24 weeks
SA Outcomes							
Timeline follow-back for SA	Father and Mother	.91		X	X	X	X
Urinalysis Drug Panel	Father	NA	X	X		X	X
IPV Outcomes							
Conflict Tactics Scale Revised (CTS2)	Father and Mother	.79 to .95	X				X
Timeline follow-back for IPV	Father and Mother	.91		X	X	X	X
Court and Arrest Records	N/A	N/A	X				X
CM Risk Outcomes							
Parental Reflective Functioning Questionnaire (PRFQ)	Father	.82	X			X	X
Adult Adolescent Parenting Inventory (AAPI)	Father and Mother	.74 to .98	X			X	X
Father-Child Free Play coded using (CIB)+	Blind Coders						X
Quality of Co-Parental Relationship Scale	Father and Mother	F: .66 - .88 M: .80 - .83	X			X	X
Satisfaction Outcomes							
Client Satisfaction Questionnaire 8	Father	N/A				X	
Mediators							
Articulated Thoughts in Stimulated Situations (ATSS) and HR/SC	Blind Coders	N/A	X		X		
Difficulties in Emotion Regulation Scale (DERS)	Father	.93	X		X	X	X
State-Trait Anger Inventory (Staxi)	Father	.84 - .93	X		X	X	X
Rumination-Reflection Scale (ARQ)	Father	.88 - .91	X		X	X	

Working Alliance Inventory	Father and Clinician	.79 - .97		X			
Motivation to Change (URICA-DV)	Father	.85 - .87		X			
Moderators							
Childhood Trauma Questionnaire	Father	.80 - .97	X				
Self-Report Psychopathy Scale 3	Father	.60	X				
Life Change Index Scale	Father	N/A	X				X
Brief Symptom Inventory (BSI)	Father	.74 - .89	X			X	X
Addiction Severity Index	Father	.89	X				
Father Interview	RA	N/A	X			X	X
Treatment Services Review	Father	N/A				X	X
PhenX Measure: Self-Report HIV Testing	Father	N/A	X				
FRPN FATHER ENGAGEMENT SCALE_v1	Father	N/A				X	X
FRPN FATHER ENGAGEMENT SCALE_v2	Father	N/A				X	X
FRPN FATHER ENGAGEMENT SCALE_v3	Father	N/A				X	X
Measure of Contact-Fatherhood Research and Practice Network	Father	N/A				X	X
Domestic Violence Quiz	Father	N/A	X		X		
Co-Parenting Quiz	Father	N/A	X		X		

At the 3 month follow-up, fathers will be asked to attend a play assessment with their child. This will be a 30 minute appointment in which they will play with toys or games with their child for 15 minutes, clean up and then complete several puzzles with their child. These session will be audio recorded and coded using the Child Interactive Behavior Rating Scale by trained blind coders.

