The PI, co-investigator [name], and study coordinator will be the only ones who have access to the data, and data will be stored in locked file cabinets and on password protected computers. Data will be analyzed in aggregate to investigate study hypothesis (stated above).

Urinalysis Data Collection

To ensure urine screening data is available for all participants, including those who are no longer receiving services and providing urine samples at Westcare, Inc., or Salvation Army, any participants who have not given urine drug screens at Westcare Inc. or Salvation Army within a week of the post-treatment and 3 month follow-up assessments, Integrated iCups from Instant Technologies will be used for urine drug screening at the time of their assessment interviews. RAs will provide clean test cups taken from the packaging just prior to collection. Participants will be asked to provide the urine sample at the end of the assessment session. They will go into a private bathroom at the location of the interview. They will be instructed to place the sample in the cup and close it. RAs will wear rubber gloves when handling test samples. They will immediately read the urine test results by peeling the test panel on the side of the cup and reading the results. They will document the results on the Urine Screening Form. The urine sample and rubber gloves will be immediately disposed of in the waste bin at the location.

Sample Size

The study will be recruiting 60 male participants that are in a 6 month residential treatment, their female co-parents (youngest child's mother) and their youngest child for a total sample of 180.

Study Population

Sixty male participants of the WestCare Community Involvement Center or the Salvation Army Adult Rehabilitation Center who are residents.

Inclusion criteria: 1. Is the father (biological or adoptive) of a child under 15 years old (including an unborn fetus expected in the next 6 months); 2. Reports some verbal or physical aggression in his current or former co-parenting relationship; 3. Is diagnosed with substance use of alcohol, cocaine, amphetamines, opiates, marijuana at the time of intake at Westcare or Salvation Army.

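### A father can qualify through one child but be assessed on another, because the target child is chosen by age alone and need not be one he had qualifying contact with

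*Protocol*

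**What the plan says.** The inclusion criteria in the Study Design section of the protocol admit a father who is expecting his first child, or who satisfies a contact condition for one or more of his biological children under 15. The condition is worded "lived or had at least once per month contact prior to admission to Westcare or Salvation Army". One qualifying child is enough.

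The same paragraph then sets the target: "If a participant has more than one child in the age range, the youngest child will be the target of assessment". Contact is not mentioned. The informant follows from that choice: "Female co-parents (the target children's mothers) will be invited to participate as collateral informants on research assessments".

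The recruitment text earlier in Study Design agrees ("Mothers of the father's youngest child will be recruited in several ways"). So do the Sample Size section and the closing sentence of Study Population, both of which identify child and mother by the word youngest alone.

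Study Population also has its own inclusion list, whose first item reads "Is the father (biological or adoptive) of a child under 15 years old (including an unborn fetus expected in the next 6 months". That list has no contact requirement at all.

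Table 1 schedules a coded father-child play session at the 3-month follow-up only. The text below it says "At the 3 month follow-up, fathers will be asked to attend a play assessment with their child", without stating which child. The co-parental relationship scale is rated by father and mother at baseline, 16 and 24 weeks.

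**The concern.** The contact condition presumably exists so that there is an active father-child relationship to treat and measure. The target rule does not carry it forward. Take a man who lived with his 9-year-old and has a 2-year-old by another woman, whom he sees less than monthly. He qualifies through the older child. The younger child is the target, and her mother is the informant.

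For such a father the play session may not take place, or may record an interaction with a child he hardly knows. The co-parental scale would describe a partnership with little activity, and the mother may be harder to recruit or have little to report on the follow-back and the CTS2. If this affects more than a few fathers, the play and co-parent comparisons lose observations, or include observations in which a treatment difference is harder to see.

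**Working it through.** **The plan's own figure.** Sample Size gives a total of 180. One father, one co-parent and one youngest child per family: 60 × 3 = 180. This reproduces, and it confirms that one youngest child and that child's mother are counted per father. The documents give no power calculation, effect size or dropout rate to check.

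**The rules side by side.**

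| Place in protocol | What is fixed | Contact condition? |
|---|---|---|
| Study Design, criterion 3 | Eligibility | Yes, for at least one child |
| Study Design, target sentence | Child assessed | No, youngest in age range |
| Study Design, recruitment of mothers | Co-parent | No, mother of youngest |
| Sample Size | Co-parent and child counted | No, youngest |
| Study Population, item 1 | Eligibility | No |
| Study Population, closing sentence | Co-parent and child | No, youngest |

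Under the Study Design list, a mismatch needs a father with two or more children in range whose youngest is not one he had qualifying contact with. If both children have the same mother, the child changes but the informant does not. Under the Study Population list, even a father of one child could be enrolled without qualifying contact.

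**What could close the gap.** The interest form asks about contact with the children, but no rule uses the answer to choose the target. The contact measure in Table 1 is scheduled at 16 and 24 weeks, not at baseline. The SAP does not say how fathers without contact with the target child are handled.

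**Size, for illustration.** The affected share f is not in the documents; 10%, 20% and 30% are assumptions. Also assumed: 30 per arm, and the SAP's .10 level taken as two-sided (it does not state sidedness).

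- Fathers affected: 60 × f = 6, 12, 18.
- Detectable standardized difference at 80% power: (1.645 + 0.842) × √(2/n). At n = 30 this is 0.64.
- Pairs missing: n = 30(1 − f), power = Φ(0.642 × √(n/2) − 1.645).
- Pairs measured but showing no effect: n = 30, power = Φ(0.642(1 − f) × √(30/2) − 1.645).

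| f | Pairs per arm if missing | Detectable difference if missing | Power if missing | Power if measured with no effect |
|---|---|---|---|---|
| 0 | 30 | 0.64 | 80% | 80% |
| 10% | 27 | 0.68 | 76% | 72% |
| 20% | 24 | 0.72 | 72% | 64% |
| 30% | 21 | 0.77 | 67% | 54% |

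The last column is a worst case, since nothing in the documents shows that these fathers would gain nothing. Thirty pairs per arm is also optimistic: fathers are enrolled when the co-parent declines, and a man expecting his first child may have no child, or only a newborn, at 24 weeks.

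**The case against.** The age-range wording directly follows criterion 3 and could be shorthand for children who meet the whole criterion. That is possible, but the sentence states age only, and every other place uses youngest with no qualifier. If contact was meant, one clause should say so.

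There are safeguards. Men with an active full no-contact order covering partner or child are excluded, each father must agree to co-parent contact and supply her details, and the mother may be screened by phone on violence history and willingness. These narrow the gap. They do not close it: a man can supply a mother's details and have no order against him while rarely seeing the child.

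A reader might infer that mismatched fathers have no relationship with the target child and cannot respond to treatment. The documents do not support that. Missing the criterion means he neither lived with the child nor had at least monthly contact before admission. The Study Design description of Fathers for Change includes repairing the father-child relationship, covers co-parenting topics whether or not the mother attends, and allows delivery to the father alone.

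A reader might also infer that hypothesis 4 as a whole is compromised. It is not. Table 1 also has father-reported CTS2 and follow-back, court and arrest records, and father-rated PRFQ and AAPI, and nothing ties these to contact with the youngest child. Table 1 does not say whose parenting the mother rates on the AAPI. For her CTS2 and follow-back, what matters is her own contact with the father, which a child-contact rule addresses only indirectly.

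**Conclusion.** The gap is real on the plain text: eligibility depends on contact with at least one child, while the target child and informant are chosen by age. The clear exposure is the single play session and the co-parental relationship scale, with a lesser exposure for the mother-reported CTS2 and follow-back. Completion, urinalysis, DERS, STAXI, records and father-reported outcomes are not clearly affected.

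It would be tempting to read this as a bias in favour of one arm. The documents do not support that: the child is fixed by a rule that does not depend on assignment, and fathers are randomized after baseline. The expected harm is missing data and dilution.

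Its frequency is unknown. The 10% to 30% range and the resulting power figures are assumptions that show scale only, and 60 is an upper bound on usable pairs. In a pilot of feasibility and signal this should be corrected, but it does not undermine the trial.

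**What to change.** - In Study Design, state that where a father has more than one child in the age range, the target is the youngest child who meets the residence or monthly-contact requirement.
- Define the co-parent as that child's mother wherever youngest is now used: Study Design (recruitment and inclusion text), Sample Size, and the closing sentence of Study Population.
- Reconcile the Study Population inclusion list with Study Design. Otherwise a father admitted under the former with no qualifying contact would have no target under the new rule.
- Record residence and contact for each child at screening. The present form asks about children collectively.

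The SAP is written in the past tense, so enrolment may be complete. In that case, report by arm how many fathers lacked qualifying contact with the target child, where records allow, and repeat the play and co-parent analyses without them as a sensitivity analysis.

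The cost is a few sentences and one screening item. Some target children will be older, and contact will rest largely on the father's report, which is less objective than age. The rule is still set before randomization. It does not ensure that the informant is the partner in the qualifying violent relationship, because the Study Design violence criterion asks only that he "report physical or psychological violence in an intimate relationship within 12 months of admission to the program".

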Official Study Title:

Intimate Partner Violence and Fatherhood Intervention in Residential Substance Abuse Treatment

NCT Number: NCT02979262

Date Last Modified: 8/14/2017

IRB approval: 8/27/2018

Project Title

Intimate Partner Violence and Fatherhood Intervention in Residential Substance Abuse Treatment

Study Rationale and Background Information

Substance use and intimate partner violence (IPV) are two severe problems that often co-occur (Centers for Disease Control & Prevention, 2013; Centers for Disease Control, 2012; Shorey, Stuart, & Cornelius, 2011) and can lead to poor parenting behaviors (Gustaffson & Cox, 2012; McMahon, Winkel, & Rounsville, 2008). Current treatments for co-occurring substance abuse and IPV are lacking ([name], 2013). This study will test initial efficacy of a novel intervention for IPV and substance use among fathers in residential substance abuse treatment: Fathers for Change compared to a standard parenting intervention.

Research Hypotheses

This initial pilot will assess the feasibility, acceptability, and intervention signal of Fathers for Change compared to a Parent Education Condition within a residential treatment center for substance dependent men. We will test the following specific hypotheses:

1. Fathers in the Fathers For Change (FFC) group will have comparatively greater completion rates in both the residential and aftercare components of the program compared to fathers in the Dads 'n' Kids (parenting education-PE) program.
2. Fathers in the FFC group will exhibit greater improvement in hostile cognitions, emotion regulation and physiological arousal at the time of residential treatment discharge (12 weeks) and following aftercare sessions (16 weeks) than fathers in the Dads 'n' Kids group.
3. Men in the FFC group will experience comparatively less substance abuse relapse at the 3 month-follow-up than in the Dads 'n' Kids group.
4. Men in the FFC group will report fewer intimate partner violence (IPV) incidents and CM risk behaviors at 24 week follow-up than fathers in the Dads 'n' Kids group.
5. Exploratory Hypothesis: The relationship of Intervention (FFC versus PE) to substance abuse relapse, IPV, and child maltreatment risk behavior (at 24 week follow-up) will be mediated by reductions in hostile cognitions and emotion regulation (measured at 16 weeks).

Study Design

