Official Study Title:

Intimate Partner Violence and Fatherhood Intervention in Residential Substance Abuse Treatment

NCT Number: NCT02979262

Date Last Modified: 3/25/2019

Data analysis Plan

Because the variables of interest involved a mix of continuous, count, dichotomous, and multinomial variables, generalized linear modeling techniques were used to test for between group differences in the demographic and clinical characteristics of the participants, the process outcomes, and the secondary outcomes only measured once or twice at the end of treatment or the end of the 3-month period of follow-up. Similarly, generalized estimating equations (GEE), the repeated-measures extension of generalized linear modeling, was used to test for between group differences in baseline values, within-group change over time, and between-group differences in the rate of change for primary and secondary outcomes measured two to five times from randomization through the 3-month period of follow-up. When there were only two measurements, time was dummy coded to represent the first and second measurements. When there were three or more measurements, time was coded as a continuous variable representing weeks from randomization. Consistent with the CONSORT recommendations, process, primary, secondary, and end-point outcomes were analyzed for both the intention-to-treat and per-protocol samples.

Across statistical analyses, dummy coding was used to represent facility and treatment assignment; and preliminary analysis of descriptive statistics, graphical representation, and goodness of fit statistics were used to determine the appropriate response distribution and link function for use in the final analysis of each dependent variable. When it was not fixed at 1.0, the deviance/df statistic was used to determine the dispersion parameter. Given the limited sample size and the potential costs of a Type II error in this type of pilot study, statistics with p values less than .10 were considered statistically significant. Despite this, there was a focus on the consistency of findings across variables and intention-to-treat versus per-protocol samples.

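### No baseline timeline follow-back is scheduled, so the SAP's baseline and rate-of-change tests for it would rest on extrapolation to week 0

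*Protocol*

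**What the plan says.** **Schedule.** In protocol Table 1, "Timeline follow-back for SA" and "Timeline follow-back for IPV" are both rated by father and mother. Both are blank at baseline and marked monthly and at 12, 16 and 24 weeks. The other substance-use and IPV outcomes do have a baseline mark: "Urinalysis Drug Panel", the revised Conflict Tactics Scale (CTS2) and "Court and Arrest Records". The Addiction Severity Index (ASI), listed among the moderators, is also taken at baseline.

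**Narrative.** The Study Design section of the protocol describes the monthly interviews as covering motivation and alliance, and does not mention follow-back. It has co-parents assessed at baseline and at the 3-month follow-up only. Randomization follows the baseline assessments, and therapy is weekly. No look-back window for follow-back is stated.

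**Analysis.** For primary and secondary outcomes measured two to five times, the SAP uses GEE to "test for between group differences in baseline values, within-group change over time, and between-group differences in the rate of change". With three or more measurements, time is continuous, in weeks since randomization. Secondary outcomes measured only once or twice, late in the trial, go to a generalized linear model. No instrument is assigned to either route by name.

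**Hypotheses.** Hypothesis 3 reads "Men in the FFC group will experience comparatively less substance abuse relapse at the 3 month-follow-up than in the Dads 'n' Kids group". Hypothesis 4 begins "Men in the FFC group will report fewer intimate partner violence (IPV) incidents and CM risk behaviors at 24 week follow-up". Both compare arms at follow-up.

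**The concern.** A model with time in weeks since randomization defines its baseline difference at week 0. For follow-back, nothing is scheduled there, so the fitted line must be carried back from values collected after weekly therapy has started. An effect that appears before the first assessment can then be reported, in part or in full, as a difference the arms had at the start, and the rate-of-change test can miss it.

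This matters because follow-back is the only IPV outcome scheduled between baseline and week 24, and the only substance-use outcome with a mother's report. A baseline score on the same instrument is also unavailable as a covariate, which costs some precision in a trial of 60 fathers.

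**Working it through.** The documents give no power or variance figure to reproduce. The check has four steps. Steps 2 and 3 are straight-line illustrations, not predictions for this trial.

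**1. Which SAP route applies.**
- Table 1, with monthly visits assumed at weeks 4, 8, 12 and 16: distinct times 4, 8, 12, 16 and 24, so five measurements.
- Study Design narrative, with no monthly follow-back: weeks 12, 16 and 24, so three measurements.

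Both counts lie within two to five and call for continuous time. The father's follow-back therefore falls in the GEE class on either reading. The mother's, on the narrative, has a single value at week 24 and does not.

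**2. Where an early effect goes.** Fit the arm difference by least squares: slope = Sxy/Sxx, intercept = mean(y) − slope × mean(t). The true difference at week 0 is zero.

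*Times 4, 8, 12, 16, 24:* mean 12.8, Sxx = 1056 − 5 × 12.8² = 236.8. *With week 0 added:* mean 10.667, Sxx = 1056 − 6 × 10.667² = 373.3.

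*Times 12, 16, 24:* mean 17.333, Sxx = 976 − 3 × 17.333² = 74.67. *With week 0 added:* mean 13, Sxx = 976 − 4 × 13² = 300.

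| True arm difference | Times fitted | Slope per week | Apparent baseline difference |
|---|---|---|---|
| 1 unit, complete before week 4, then flat | 4 to 24 | 0 | 1.00 |
| same | 0 to 24 | 10.667/373.3 = 0.029 | 0.53 |
| Builds evenly to 1 unit at week 16, then flat | 4 to 24 | 9.2/236.8 = 0.039 | 0.20 |
| same | 0 to 24 | 16.667/373.3 = 0.045 | 0.11 |
| same | 12, 16, 24 | 1.333/74.67 = 0.018 | 0.61 |

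For the last row, y = 0.75, 1, 1 with mean 0.917. Sxy = 49 − 3 × 17.333 × 0.917 = 1.333, and the intercept is 0.917 − 0.0179 × 17.333 = 0.61.

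The size of the problem thus depends on how early the effect arises and when follow-back starts. Adding week 0 as another outcome point does not fully cure it: in the second row the straight line still assigns 0.53 to baseline.

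**3. Precision of the baseline and slope terms.** Assume equal variances and exchangeable correlation ρ. The slope's standard error is then proportional to 1/√Sxx.
- First follow-back at week 4: √(373.3/236.8) = 1.26 times as large without week 0.
- First follow-back at week 12: √(300/74.67) = 2.00 times as large.

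The intercept variance is proportional to (1 − ρ)(1/k + mean(t)²/Sxx) + ρ, where k is the number of times. For ρ from 0.7 down to 0.1, the standard-error ratio runs from 1.07 to 1.31 (week-4 start) and from 1.46 to 2.20 (week-12 start).

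**4. Precision of the between-arm comparison.** With 30 fathers per arm (equal split assumed), chance imbalance in a standardized pre-admission score has SD √(2/30) = 0.26, or ±0.51 at 95%. At an assumed correlation r of 0.3 to 0.5 with the outcome, this shifts the outcome by 0.51 × 0.3 = 0.15 to 0.51 × 0.5 = 0.25 SD. Adjustment removes r², or 9% to 25%, of outcome variance in a linear model. The equivalent sample is 60/0.91 = 65.9 to 60/0.75 = 80, about 6 to 20 more fathers.

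**The case against.** **The SAP never says follow-back enters the GEE.** True. The assignment is inferred from the measurement count. But the SAP sorts outcomes by count, and neither three nor five measurements fits its once-or-twice alternative.

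**Randomization protects the follow-up comparison.** True. A reader might infer that, without a baseline score, the tests of Hypotheses 3 and 4 are confounded. The documents do not support that. Both hypotheses compare randomized arms at follow-up, and chance imbalance is already part of the standard error.

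**Both domains have other baseline measures.** Largely right. ASI and urinalysis for use, and CTS2 for IPV, can serve as covariates, because a covariate need not share the outcome's scale. They cannot supply a week-0 value on the follow-back scale. The 6 to 20 father-equivalents are therefore an upper figure, relative to no adjustment. The further gain from a follow-back baseline would be smaller, and the linear formula is only a guide for count or dichotomous outcomes.

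**An early effect is not always lost.** Also right. With a week-4 start, an effect that builds evenly to week 16 is mostly kept in the slope.

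**The timing is uncertain.** It is. Week 4 rests on Table 1's monthly column, which the Study Design narrative does not support for follow-back. With no stated window, the first administration might reach back before treatment, but the plan does not say so, and that recall would still be taken after therapy began.

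**Conclusion.** The point holds for the SAP's baseline and change tests as applied to follow-back, and for precision. Neither follow-back instrument has a scheduled pre-treatment administration, so a GEE baseline difference for it would be an extrapolation from on-treatment data. An effect arising before the first assessment could appear partly or wholly as that difference.

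Two stronger readings fail. One is that the analysis starts from a month-1 value; with time in weeks since randomization, the baseline term refers to week 0. The other is that the trial has no baseline information on substance use or IPV; Table 1 shows that it does.

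The conclusion rests on the inferred GEE assignment, the assumed monthly visit weeks and the straight-line illustration. The gap should be corrected, but it does not undermine the randomized comparisons at follow-up.

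**What to change.** 1. **SAP.** State that follow-back is analysed as between-arm differences over defined post-randomization periods, including 24 weeks. Adjust for facility and for baseline measures already collected: ASI and urinalysis for use, CTS2 for IPV. Report no baseline difference and no change from baseline for follow-back. This needs only SAP wording and no new data, so it remains usable although the SAP, dated 3/25/2019, is written in the past tense.
2. **Table 1, where enrolment still allows.** Add both follow-back instruments to the existing father and co-parent baseline interviews, with one fixed window before admission, and use that score as the covariate. The cost is added interview time: baselines already take about 2 hours for men and 1 hour for women. No new visit is needed.
3. **Reconcile the schedule.** Table 1 has monthly follow-back from father and mother. The Study Design narrative gives the monthly interviews other content and assesses co-parents only at baseline and the 3-month follow-up. State which applies, and give the look-back window for each administration. This is an editorial change.
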